## 6. Final Power Assessment

Date conducted: 12/22/2020

- Re-calculate power in the appropriate excel table, using the revised number of matched patients from the PS-match in Section 9. All other parameters in the table should be the same as in Section 8.

Superiority Analysis (Pooled)	
Number of patients matched	
Reference	3,033
Exposed	3,033
Risk per 1,000 patients	215.25
Desired HR from RCT	0.8
Alpha (2-sided)	0.05
Number of events expected	1305.7065
Power	0.980850168

Superiority Analysis (Optum)	
Number of patients matched	
Reference	1,279
Exposed	1,279
Risk per 1,000 patients	206.60
Desired HR from RCT	0.8
Alpha (2-sided)	0.05
Number of events expected	528.4828
Power	0.727390963

Superiority Analysis ( Marketscan )	
Number of patients matched	
Reference	748
Exposed	748
Risk per 1,000 patients	160.30
Desired HR from RCT	0.8
Alpha (2-sided)	0.05
Number of events expected	239.8088
Power	0.408308308

Superiority Analysis (Medicare)	
Number of patients matched	
Reference	1,006
Exposed	1,006
Risk per 1,000 patients	248.30
Desired HR from RCT	0.8
Alpha (2-sided)	0.05
Number of events expected	499.5796
Power	0.703266933

- Stop analyses until balance and final power assessment are reviewed by primary investigators, FDA, and assigned members of advisory board.

Reviewed by PI:	[name]	Date reviewed:	12/26/20
Reviewed by FDA:		Date reviewed:	
Reasons for stopping analysis (if required):			

# Appendix A

#	PARADIGM-HF trial definitions	Implementation in routine care	Please see the following Google Drive for further details or any missing information : https://drive.google.com/drive/folders/1WD618wrywJjeXzfLTcuk-VCcnb6b-gV	
Trial details - active comparison - 2 weeks run-in			ICD-10 codes are not listed in this document because of excel cell size limitations and excessive number of ICD-10 codes. Full ICD-10 code lists will be available in the above Google Drive Folder (link above). ICD-9 to ICD-10 code conversions were completed using a SAS macro that implements forward/ backward mapping based on the CMS ICD-9 to ICD-10 mapping: https://www.nerb.org/data/icd9-icd-10-cm-and-pcs-crosswalk-general-equivalence-mapping.html	
EXPOSURE vs. COMPARISON		References/Rationale		Color coding
LCZ696 (sacubitril/valsartan) 200 mg twice daily vs. enalapril 10 mg twice daily  Aim: To determine if LCZ696 is superior to enalapril in reducing the risk of death and of hospitalization for HF		Exposure: new-use of sacubitril/valsartan Reference: enalapril		Criteria Adequate mapping in claims
PRIMARY OUTCOME				
The primary outcome is a composite of death from cardiovascular causes or hospitalization for heart failure		
Measured 14 days after drug initiation in diagnosis position specified below and inpatient care setting:
 
Hospital admission for CHF (Inpatient only, any position)
 
ICD-9 diagnosis: 428.x, 398.91, 402.01, 402.11, 402.91, 404.01, 404.11, 404.91, 404.03, 404.13, 404.93
 
ICD-10 diagnosis: I50.1, I50.2x, I50.4, I50.81, I09.81, I11.0 (hypertensive heart disease with HF), I13.0 (hypertensive heart and chronic kidney disease with HF and stage 1 through stage 4 CKD), I13.2 (hypertensive heart and CKD with HF and with stage 5 CKD or ESRD)
 
CV death
 
Inpatient mortality - heart failure --
 
Mortality- Dependent on data source.
 
 
CV mortality
 
Information on CV mortality through data linkage with the National Death Index (NDI) will be available for Medicare and Optum Clininformatics.
 
All-cause inpatient mortality
 
 
Identified using the discharge status codes- Optum-
 
 
• 20 = EXPIRED
 
• 21 = EXPIRED TO BE DEFINED AT STATE LEVEL
 
• 22 = EXPIRED TO BE DEFINED AT STATE LEVEL
 
• 23 = EXPIRED TO BE DEFINED AT STATE LEVEL
 
• 24 = EXPIRED TO BE DEFINED AT STATE LEVEL
 
		Intermediate mapping in claims
INCLUSION CRITERIA				Poor mapping or cannot be measured in claims
1	Age ≥ 18 years	Age 18 years or older at drug initiation		Can't be measured in claims but not important for the analysis
2	NYHA functional class II-IV	
Measured 45 days prior to and including the day of oral drug initiation in generic prescription claims requiring 28 days supply of Loop or Thiazide diuretics
 
Loop Diuretics: Bumetanide, Furosemide, Torsemide, Ethacrynic acid
 
-OR-
 
Thiazide and Thiazide-like Diuretics: Hydrochlorothiazide, Chlorothiazide, Chlorthalidone, Indapamide, Metolazone, Cyclothiazide, Hydroflumethiazide, Bendroflumethiazide, Benztiazide, Methyclothiazide, Polythiazide
		
3	LVEF ≤ 35%	
Measured 180 days prior to and including the day of index drug initiation in any diagnosis position and inpatient or outpatient care setting
 
Systolic Heart Failure
 
ICD-9 diagnosis: 428.2x
 
ICD-10 diagnosis: I50.2x
 
Combined Systolic/Diastolic Heart Failure
 
ICD-9 diagnosis: 428.4x
 
ICD-10 diagnosis: I50.4x
		
4	Plasma BNP ≥150 pg/mL or NT-proBNP ≥600 pg/mL at the screening visit and a hospitalization for HF within the last 12 months			
4a	Plasma BNP ≥150 pg/mL or NT-proBNP ≥600 pg/mL at the screening visit			
AND the following:				

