### 1.3 Primary endpoint for replication and RCT finding

Composite endpoint of death from cardiovascular (CV) causes or hospitalization for heart failure (HF)

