## 4. Study Design Diagram

The study design diagram visualizes key aspects of the longitudinal study design for expedited review  

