**Design Diagram – PARADIGM-HF TRIAL REPLICATION**

## 5. Cohort Identification

### 5.1 Cohort Summary

This study will involve a new user, parallel group retrospective cohort study design comparing sacubitril/valsartan to ACE inhibitors. Although the trial compared sacubitril/valsartan to enalapril, we expanded the definition of the comparator group to include all ACEi therapies to improve power, since all medications within this class of medication are indicated and guideline recommended for use in heart failure with reduced ejection fraction patients and would be expected to have similar effects on the primary outcome of CV death and HF hospitalization.

The patients will be required to have continuous enrollment during the baseline period of 180 days before initiation of sacubitril/valsartan or a ACEi (cohort entry).

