### 6.3 Outcome variables and study follow-up:

#### 6.3.1 Outcome variables

Effectiveness outcome variables of interest (definitions provided in **Appendix A**):

- **Primary outcome:** Composite of hospitalization for heart failure and all-cause mortality
- Secondary outcomes:
  - Heart failure hospitalization
  - All-cause death

Control outcomes of interest (control outcomes only serve to assess aspects of study validity but are not further interpreted, definitions provided in Appendix A):

1. Bleeding (we expect to see a null association, as renin angiotensin aldosterone inhibitors are not expected to have any impact on this outcome)

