#### 6.3.2 Study follow-up

Both as-treated (AT) and intention-to-treat (ITT) analysis will be conducted with treatment defined as the index drug on the day of cohort entry. Because adherence in the real-world databases is expected to be much worse than in the trial, the AT analysis is the **primary** analysis, as it targets the relative hazard of outcomes on treatment.

For the AT analysis, the follow-up will start the day after the initiation of sacubitril/valsartan or ACEi and will continue until the earliest date of the following events:

- The first occurrence of the outcome of interest,
- The date of end of continue registration in the database,
- End of the study period,
- Nursing home admission
  - Nursing home admissions are considered a censoring event because the data sources utilized typically provide little to no data on a patient, particularly on drug utilization, after admission. We will utilize this as an exclusion reason for cohorts for the same reason.
- The date of drug discontinuation, defined as the date of the last continuous treatment episode of the index drug (sacubitril/valsartan or ACEi) + a 30-day grace period,
- The date of switching from an exposure to comparator and vice versa,
- The date of switching to or initiation of any angiotensin II receptor blockers (ARBs), including combination medications containing ARBs,
- The date of switching to or initiation of aliskiren, including combination therapies.

For the ITT analyses, the censoring based on the switching and treatment discontinuation will be replaced with a maximum allowed follow-up time of 365 days.

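### The primary outcome has two start days (day 1 in Section 6.3.2, day 14 in Appendix A), and its death component is not stated consistently

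*Protocol*

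**What the plan says.** **Start of follow-up.** In Section 6.3.2, for the as-treated analysis, which the section names as primary, "the follow-up will start the day after the initiation of sacubitril/valsartan or ACEi". The intention-to-treat paragraph replaces the switching and discontinuation censoring with a 365-day cap. It sets no other start day.

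**Start of outcome measurement.** Section 6.3.1 introduces its outcomes with "Effectiveness outcome variables of interest (definitions provided in" Appendix A. In the routine-care implementation column there, the primary outcome is "Measured 14 days after drug initiation in diagnosis position specified below and inpatient care setting".

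**Death component.** Section 6.3.1 defines the primary outcome as "Composite of hospitalization for heart failure and all-cause mortality". The Appendix A implementation cell labels its death part as CV death and states "Mortality- Dependent on data source". It then lists CV mortality, says that National Death Index (NDI) linkage will supply it for Medicare and Optum, and lists all-cause inpatient mortality. Section 5.1 justifies the broader comparator by "similar effects on the primary outcome of CV death and HF hospitalization". The separate mortality sheet in Appendix A gives all-cause or inpatient sources by database.

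**The concern.** The two start rules count different primary events. One takes every on-treatment event from the day after initiation; the other takes only those from day 14.

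Because one rule governs follow-up and the other governs outcome measurement, both can be programmed at once. Days 1–13 would then be person-time in which no event can count. Reported rates would fall, and it would be unclear whether a patient admitted for heart failure on day 5, say, remains at risk for a later counted event.

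The scope of the 14 days is also open. The phrase refers to a diagnosis position and the inpatient setting, which suits the admission codes, but it heads a cell that also defines death.

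Median as-treated follow-up in Section 7 is only 82 to 117 days, so two weeks is a noticeable part of the risk window. The trial hazard ratio is already known, so the rule should be fixed before outcomes are analysed.

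**Working it through.** **1. The plan's own figure.** The final pooled assessment has 2 × 3,033 = 6,066 matched patients and a risk of 215.25 per 1,000, so expected events are 6,066 × 0.21525 = 1,305.7. For 1:1 groups, two-sided alpha 0.05 and HR 0.80, power = Φ(√E/2 × |ln 0.80| − 1.96) = Φ(18.07 × 0.2231 − 1.96) = 0.981. This reproduces the stated 0.98085.

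**2. Disputed window.** An event on day 14 counts under both rules, so days 1–13 are in dispute.

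**3. Early events at constant hazard.** Patients (N), events and person-years (PY) come from the Section 7 summary. The calculation assumes that those events were counted from day 1. The upper share is s = N × 13/365.25 ÷ PY, as if every patient contributed all 13 days.

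| | N | Events | PY | PY in days 1–13 | s | Early events (upper) |
|---|---|---|---|---|---|---|
| Optum | 6,930 | 1,435 | 3,277.04 | 246.7 | 7.53% | 108.0 |
| MarketScan | 3,689 | 592 | 1,877.04 | 131.3 | 7.00% | 41.4 |
| Medicare | 8,022 | 1,992 | 3,093.20 | 285.5 | 9.23% | 183.9 |
| Total | | 4,019 | | | | 333.3 (8.3%) |

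The lower quartiles of follow-up are 43, 58 and 39 days, so at least about 75% of patients contribute all 13 days. The lower figure is 0.75 × 333.3 = 250.0 (6.2%).

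**4. Other early hazards (assumption).** If the hazard in days 1–13 is r times the later one, the early share becomes r·s/(1 − s + r·s), computed per database with s and with 0.75s.
- r = 2: 470 to 615 events (11.7% to 15.3%).
- r = 0.5: 129 to 174 events (3.2% to 4.3%).

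**5. Effect on rates.** If events count from day 14 over person-time from day 1, at constant hazard and with no later counted event in the same patient, the rate is multiplied by (1 − s) or (1 − 0.75s). Per 1,000 person-years:
- Optum: 437.9 falls to 405–413.
- MarketScan: 315.4 falls to 293–299.
- Medicare: 644.0 falls to 585–599.

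**6. Effect on pooled power if every early event were lost.**
- Constant hazard: 1,305.7 × (1 − 0.083) = 1,197 events, power 0.971; 1,305.7 × (1 − 0.062) = 1,225 events, power 0.974.
- Doubled early hazard, upper share: 1,106 events, power 0.960.
- Halved early hazard, lower share: 1,264 events, power 0.978.

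**7. Which rule did the feasibility run use?** Section 7 reports only 16, 5 and 7 patients who did not begin follow-up. If time zero had been moved to day 14, early events alone should have removed about N × (1 − exp(−rate × 13/365.25)) = 107, 41 and 182 patients. Even at half the early hazard with the lower share (step 4), the figures would be about 42, 16 and 71. A delayed time zero was therefore apparently not applied. These counts cannot show whether early events were ignored while person-time ran from day 1.

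**The case against.** **The rules may be reconciled elsewhere, or a lag may be deliberate.** Section 4 says "The study design diagram visualizes key aspects of the longitudinal study design for expedited review", and that diagram is not legible in the text reviewed. Appendix A also notes the trial's two-week run-in, which could explain the 14 days. Both points are fair, but no visible text links the run-in to the outcome window. Whatever the diagram shows, the two written rules still disagree.

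**The consequences are small.** For power this stands: the pooled figure hardly moves. A reader might infer that the treatment comparison is biased. The documents do not support that. A common event-free period does not by itself bias a Cox hazard ratio, and nothing in the protocol allows a change in the hazard ratio to be computed.

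**The early hazard may be low rather than high.** Exclusion 5 removes patients with acute decompensated heart failure in the week up to initiation, so a lower early hazard is plausible. The range above therefore runs in both directions.

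**The CV-death wording may be a leftover label.** A reader might infer this because Section 7 ties the feasibility run to the Section 6.3.1 endpoint. That does support Section 6.3.1 as the governing definition. But the Appendix A cell goes beyond a label: it gives a CV-mortality definition with a planned NDI linkage. The document does not show that this text is residue, and changing the label alone would leave those lines standing.

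**Section 1.3 describes the trial.** Its heading, "Primary endpoint for replication and RCT finding", is ambiguous, but it sits under the RCT details, so its mention of CV death need not conflict with Section 6.3.1.

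**Conclusion.** The inconsistency stands and should be fixed. The protocol gives two start rules for its primary outcome and does not say whether the 14 days cover heart failure admission, death or both.

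If the Section 7 events were counted from day 1, about 6% to 8% of them depend on the rule at constant hazard, and about 3% to 15% with half to twice that hazard in days 1–13. These are events that occur early, not necessarily events lost, because a patient admitted early may have a later counted event. If the lag covers admissions only, early deaths drop out of the figure; the document does not give that split.

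It would go too far to say that the feasibility counts already leave out these events. The few patients who did not begin follow-up argue against a delayed time zero, and the counts do not settle whether early events were ignored.

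The death component is a separate inconsistency between Section 6.3.1 on one side and Section 5.1 and the Appendix A outcome cell on the other. Its size cannot be computed from the document.

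**What to change.** Before outcomes are analysed:
- State one start day for the primary outcome in both Section 6.3.2 and Appendix A, and apply it to events and person-time together.
- Say whether it covers heart failure admission, death or both.
- If a lag is intended, give the reason and say how patients with an event before day 14 are handled.
- Confirm how the Section 7 events were counted, in particular whether events in days 1–13 were included.
- Reconcile the death component across Section 6.3.1, Section 5.1 and the whole Appendix A outcome cell, including the CV-mortality and NDI lines, with the source for each database as in the Appendix A mortality sheet.

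Two additions are optional: a sentence in Section 1.3 that the replication uses the Section 6.3.1 composite, and the other start rule as a sensitivity analysis.

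The cost is wording in these sections and one check of the feasibility counts. No new data are needed.

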# Appendix A

		Measured 365 days prior to drug initiation in any diagnosis position and inpatient care setting	
4b	Hospitalization for heart failure within the last 12 months	
Hospital Admission for CHF
 
ICD-9 diagnosis: 428.x, 398.91, 402.01, 402.11, 402.91, 404.01, 404.11, 404.91, 404.03, 404.13, 404.93
 
ICD-10 diagnosis: I50.1, I50.2x, I50.4, I50.814, I09.81, I11.0, I13.0, I13.2
	
5	Treatment with a stable dose of an ACE inhibitor or an ARB equivalent to enalapril 10 mg/day for at least 4 weeks before the screening visit; and treatment with a stable dose of a beta-blocker for at least 4 weeks prior to the screening visit, unless contraindicated or not tolerated	
Measured 47 days to 2 days prior to drug initiation in prescription claims requiring 28 days supply of oral ACEi or ARB -
 
ACE inhibitors' generic names for prescription claims: Enalapril, Captopril, Clazapril, Fosinopril, Lisinopril, Moexipril, Perindopril, Quinapril, Trandolapril, Zofenopril, Benazepril
 
-OR-
 
ARBs generic names for prescription claims: Candesartan, Eprosartan, Irbesartan, Losartan, Olmesartan, Telmisartan, Valsartan, Azilsartan
	
5a	Treatment with a stable dose of an ACE inhibitor or an ARB equivalent to enalapril 10 mg/day for at least 4 weeks before the screening visit	AND the following:	
5b	Treatment with a stable dose of a beta-blocker for at least 4 weeks prior to the screening visit, unless contraindicated or not tolerated	
Measured 45 days prior to index drug initiation in prescription claims (generic names) of an oral beta-blocker for at least 4 weeks (28 days)
 
Beta-blocker generic names for prescription claims: Acebutolol, Atenolol, Betaxolol, Bisoprolol, Carvedilol, Esmolol, Labetalol, Metoprolol, Metiranolol, Nebivolol, Nadolol, Propranolol, Pindolol, Sotalol, Penbutolol, Oxprenolol
	
6	Although not required, the protocol specified that an aldosterone antagonist should also be considered in all patients, taking account of renal function, serum potassium, and tolerability. If given, the dose of aldosterone antagonist should be stable for at least 4 weeks prior to the screening visit		
EXCLUSION CRITERIA			

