# Appendix A

	Variable	Codes and Medications (all medical claims, inpatient and outpatient should be used to define the conditions unless otherwise specified)	Coefficients ("Score")	When Measured for replicating	When Measured ([name]'s algorithm)
1	Intercept	N/A	-1.37219		
2	Cardiomyopathy	ICD-9 diagnosis: 425.x ICD-10 diagnosis: I42.x, I43.x	1.415113	Measured 180 days prior to and including the date of index drug initiation	6 months prior to index date + index date + 30days post-index
3	Diastolic heart failure	ICD-9 diagnosis: 428.3x (not co-occurring with 428.2x ) ICD-10 diagnosis: I50.3x (not co-occurring with I50.2x)	-0.950856	Measured between 180 days prior to and including the date of drug initiation and pick claim closest to the index initiation	on index date
4	Left heart failure	ICD-9 diagnosis: 428.1x (not co-occurring with more specific systolic or diastolic HF codes of 428.2x or 428.3x) ICD-10 diagnosis: I50.1 (not co-occurring with more specific systolic or diastolic HF codes of I50.2x or I50.3x)	0.766415	Measured between 180 days prior to and including the date of drug initiation and pick claim closest to the index initiation	on index date
5	Systolic heart failure	ICD-9 diagnosis: 428.2x (not co-occurring with 428.3x) ICD-10 diagnosis: I50.2x (not co-occurring with I50.3x)	0.754954	Measured between 180 days prior to and including the date of drug initiation and pick claim closest to the index initiation	on index date
6	Myocardial infarction	ICD-9 diagnosis: 410.xx ICD-10 diagnosis: I21.01, I21.02, I21.09, I21.11, I21.19, I21.21, I21.29, I21.3, I21.4, I22.0, I22.1, I22.2, I22.8, I22.9	0.651778	Measured 180 days prior to and including the date of index drug initiation	6 months prior to index date + index date + 30days post-index
7	Unspecified heart failure	ICD-9 diagnosis: 428.0x, 428.4x, 428.9x, 428.2x PLUS 428.3x ICD-10 diagnosis: I50.4x, I50.8x, I50.9, I50.2x PLUS I50.3x	-0.577221	Measured between 180 days prior to and including the date of drug initiation and pick claim closest to the index initiation	on index date

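### As printed, the ICD-10 list for heart failure hospitalization omits I50.3x and I50.9 although the ICD-9 list takes all of 428.x, in both the primary outcome and Inclusion #4b

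*Protocol*

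**What the plan says.** In Appendix A, the HF component of the primary outcome is an inpatient diagnosis in any position: "Hospital admission for CHF (Inpatient only, any position". The ICD-9 definition is "ICD-9 diagnosis: 428.x, 398.91, 402.01, 402.11, 402.91, 404.01, 404.11, 404.91, 404.03, 404.13, 404.93", which takes the whole of 428. The ICD-10 definition starts "ICD-10 diagnosis: I50.1, I50.2x, I50.4, I50.81, I09.81, I11.0" and then adds I13.0 and I13.2.

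Inclusion #4b (HF admission in the prior 12 months) has the same ICD-9 list and gives "ICD-10 diagnosis: I50.1, I50.2x, I50.4, I50.814, I09.81, I11.0, I13.0, I13.2". The algorithm table that predicts ejection-fraction class uses nearly the same short ICD-10 list in item 8 (number of HF hospitalizations) and item 12 (outpatient index diagnosis).

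The same algorithm table also shows how its authors match the two code sets. Item 3 defines diastolic HF by 428.3x and by I50.3x. Item 7 defines unspecified HF by "428.0x, 428.4x, 428.9x, 428.2x PLUS 428.3x" in ICD-9 and by "I50.4x, I50.8x, I50.9, I50.2x PLUS I50.3x" in ICD-10.

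The header of Appendix A says that full ICD-10 lists are kept in an external folder and that "ICD-9 to ICD-10 code conversions were completed using a SAS macro".

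**The concern.** Two definitions of one event should count the same admissions. Here the ICD-9 side takes every HF type and the ICD-10 side, as printed, does not. What counts as a primary event, and who satisfies #4b, then depends on the code set in force on the date of the stay.

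The study is meant to reproduce a trial endpoint of HF hospitalization or cardiovascular death, and the protocol gives no reason for a narrower HF definition under ICD-10. An analyst who follows the printed cells would drop stays that the ICD-9 definition shows were meant to count.

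**Working it through.** **1. The lists side by side.** The counterparts in the second column are those that Appendix A itself prints.

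| ICD-9 group within 428.x | ICD-10 counterpart and where it is printed | Primary outcome list | Inclusion #4b list |
|---|---|---|---|
| 428.1 | I50.1 (algorithm item 4) | present | present |
| 428.2x | I50.2x (Inclusion #3, item 5) | present | present |
| 428.4x | I50.4x (Inclusion #3) | printed as I50.4 | printed as I50.4 |
| 428.3x | I50.3x (item 3) | **absent** | **absent** |
| 428.0x, 428.9x | I50.8x and I50.9 (item 7) | I50.81 only; **I50.9 absent** | I50.814 only; **I50.9 absent** |

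For the last row, take out of item 7 the 428.4x/I50.4x pair and the combined systolic-plus-diastolic pair. That leaves 428.0x and 428.9x on one side and I50.8x and I50.9 on the other.

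**2. Consistency of the short list.** The outcome has I50.81; #4b and items 8 and 12 have I50.814. The outcome, #4b and item 8 have I50.4; item 12 and Inclusion #3 have I50.4x. Exclusion #5 uses the longer codes I50.41 and I50.43, so a literal I50.4 is not a safe shorthand.

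**3. The rule applied.** A stay coded only 428.0 or 428.3x counts under ICD-9. A stay coded only I50.9 or I50.3x does not count under the printed ICD-10 list, either as an event or for #4b.

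**4. How much is lost.** A stay with I50.3x or I50.9 is still caught if I11.0, I13.0, I13.2 or another listed code appears in any position. Appendix B shows recorded hypertension in about 88% to 97% of matched patients, so many such stays may be caught. That is not a bound, since baseline hypertension does not fix how a later stay is coded. The protocol gives no share of stays that carry only an omitted code, so the loss cannot be computed.

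**5. Power.** The plan's final pooled figure reproduces.

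- Risk from counts already observed (Sections 7 and 8): (1,435 + 592 + 1,992) / 18,671 = 4,019 / 18,671 = 215.25 per 1,000.
- Expected events: 2 × 3,033 × 0.21525 = 1,305.7.
- Power = Φ(|ln 0.8| × √1,305.7 / 2 − 1.96) = 0.981, against 0.98085 stated.

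There are two cases. If the short list was run, these counts are already net of the omission; for a fixed cohort, adding codes to the outcome list can only raise them. If the full list was run, nothing changes. As an assumed illustration at 3,033 pairs:

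| Assumed rise in composite events | Events | Power at HR 0.80 |
|---|---|---|
| 0% | 1,305.7 | 0.981 |
| 10% | 1,436.3 | 0.988 |
| 20% | 1,566.8 | 0.993 |
| 30% | 1,697.4 | 0.996 |

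Widening #4b would also change who enters the cohort and how many pairs match; the documents do not allow that to be projected.

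**The case against.** The strongest reply is that the printed cells are abbreviations. The Appendix A header says complete ICD-10 lists are held elsewhere and were produced by forward and backward mapping, so the list actually run may contain I50.3x and I50.9. This stands in part: nobody can say from the protocol that events were in fact missed. It does not remove the point, because these cells do print explicit ICD-10 lists, and those lists disagree with each other. If the folder differs, the protocol misstates its primary outcome; if it agrees, the outcome is narrower than under ICD-9.

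A second reply is that the narrowing is deliberate, because the target population has reduced ejection fraction. Whether purely diastolic admissions should count is a fair design question, but no such reason is given. The ICD-9 side includes diastolic HF, and the argument would not explain dropping unspecified HF.

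A reader might infer more than the documents support:

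- **Lost power.** Step 5 shows that the counts behind the power are observed. HF codes also leave the all-cause death component of the composite untouched, so a share of HF events cannot simply be taken off all events.
- **Bias between arms.** Nothing shows coding that differs by arm. After matching, baseline HF hospitalization is close (81.4% vs 82.2%, 80.5% vs 79.3% and 73.9% vs 73.6% in Optum, MarketScan and Medicare). So is entry in 2015–2016 (11.4% vs 12.0%, 30.6% vs 31.1%, 35.3% vs 37.2%).
- **Skewed selection of the reference group.** The flowchart applies the algorithm to that group only, and items 8 and 12 use the short list. But their coefficients have opposite signs (0.346 and −0.187), so the direction of any effect is not fixed.
- **Large wrongful exclusion at #4b.** That step removes 40.6% (9,321/22,938), 41.6% (4,618/11,100) and 27.2% (10,685/39,247). These are all patients without a qualifying admission; nothing attributes any of them to omitted codes.

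**Conclusion.** The point holds as an error in the printed definitions of the primary outcome and Inclusion #4b: the ICD-10 list is not equivalent to 428.x by the protocol's own pairing of codes, and it varies from place to place. The effect is under-capture of stays coded only as diastolic or unspecified HF. It is partial and cannot be sized from the protocol. It is a matter of what the outcome and eligibility rule mean, not of pooled power or of a demonstrated bias in the hazard ratio. The conclusion assumes that the printed cells are meant to be followed; whether the analysis used them can be settled only from the external folder.

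**What to change.** Print one ICD-10 list equivalent to 428.x, identically in the primary outcome and in Inclusion #4b: I50.x (including I50.3x, I50.4x, I50.8x and I50.9) plus I09.81, I11.0, I13.0 and I13.2. Confirm it against the operative list in the external folder and state which list was run. If diastolic-only stays are to be left out on purpose, say so, give the reason, and apply it to the ICD-9 list as well.

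Algorithm items 8 and 12 carry fixed coefficients from a cited model. Reconcile their code lists with that model's own definition rather than redefining them to match the outcome.

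Cost: if the full list was run, only the text changes. If the short list was run, no new data are needed, but the flowchart, propensity-score matching, balance tables, arm-blinded event count and power tables must be regenerated and go back through the reviews that the protocol requires after Section 8 and after the Final Power Assessment.
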